### **Stopping Rules for Efficacy and Safety**

In the case of withdrawal from the study, a subject will continue to be monitored even after he/she has discontinued study medications. If at the end of the study the subject is transferred to the care of a different psychiatrist, the study doctor will fully inform the new treating psychiatrist of the details of the subject's study involvement in order to provide continuity of care and for the subject's health and safety. Information regarding study participants will not leave the institution in any form that would identify an individual participant. Participants will be identified by code only. All files will be kept within locked cabinets or access-restricted computer networks within the institution. A Certificate of Confidentiality will be obtained to protect participant information. All procedures will comply with the Health Insurance Portability and Accountability Act (HIPAA).

A participant may withdraw their consent at any time. To have their specimen and information removed from the Bipolar Biobank, they must do so in writing. Withdrawal from the Bipolar Biobank will not affect any studies already conducted or those which have already received sample and/or information from the Bipolar Biobank.

### **Inclusion of Minorities**

We recognize the importance of inclusion of minorities in medical research. The influence of ethnicity on the representation of specific polymorphisms in different ethnic and racial groups and their effects on response to medications is important. Participants of all ethnic and racial categories will be included. If results of this study clarify the role of polymorphisms in the genes that will be studied for treatment response, studies could be designed to address the possible role of these polymorphisms in minority groups. Collaboration with other research facilities would be required in order to achieve this goal, given the demographic characteristics of southeastern Minnesota.

**Individual Participant Stopping Rules (if applicable):** A subject has the right to withdraw consent at any point during the study. The investigator reserves the right to discontinue a subject's participation in this study at any time.

### **DSMB: Data & Safety Monitoring Plan (DSMP)**

Per protocol guidelines, study participants must meet all inclusion criteria and none of the exclusion criteria. All criteria will be reviewed by the study coordinator and PI prior to commencement of study drug. The PI and study coordinator will meet on a weekly basis.

#### **1. Subject Safety**

Safety monitoring will be undertaken by a committee integrated by psychiatrists outside of this protocol consisting of: [name] M.D. Chair, Mayo Clinic Arizona; [name]., George Washington University and Director, Bipolar Collaborative Network; and [name]., FRCPC, University of Calgary. The DSMB will meet twice per year by phone with [name] and [name]. The DSMB Board will review enrollment numbers, demographics, serious adverse events, CGI outcomes, and publications based on biobank data. There is no blind so there is no need for unbinding outcome data.

#### **2. Data Integrity**

RAVE® platform will be utilized for data collection by all centers. Data integrity will be managed by the project manager working with the study coordinator and supervised by the PI, in coordination with RAVE®.

#### **3. Subject Privacy**

Participants will be identified by a deidentified code only. All files will be kept within locked cabinets or access-restricted computer networks within the institution. A Certificate of Confidentiality will be obtained to protect participant information. All procedures will comply with the Health Insurance Portability and Accountability Act (HIPAA).

#### 4. Data Confidentiality

The research data for this study will be shared as part of the NIH Data Share policy. All participants will be identified by a unique enrollment identification number that will maintain their anonymity. All shared data will be coded by this I.D. All personal information will be kept separate and locked in a file only accessible by the Principal Investigators. There will be no participant identifiers in the subject casebook.

#### 5. Product Accountability

Medication will be stored with the Mayo Clinic Pharmacy. All prescriptions will be signed by a study doctor and picked up by a member of the study team.

#### 6. Study Coordination

This study will be overseen by a Principal Investigator (PI), co-investigators, project manager, and a designated study coordinator. Every week, the PI, project manager, and the study coordinator will review the following information in detail at the study meeting:

- 1) Subject recruitment rate
- 2) Subject drop-out and the reasons for drop-out
- 3) Side effects and mood ratings per subject visit
- 4) Subject compliance with the protocol
- 5) Study coordinator questions or concerns

#### Questionnaires that ask about Depression (if applicable)

Included in study? Yes  No

#### If "Yes", state the plan of management for participants with possible depression:

There are no known risks to the participants participating in mood interviews. The material covered is based on standard clinical care and consists of questions that they would be asked by the psychiatrists under normal clinical care. Standardized instruments will be administered. Participants are asked to answer questions on a voluntary basis and are told that uncomfortable questions do not have to be answered.

All questionnaires that involve questions related to depression and/or harm to self or others will be reviewed within 1 working day of receipt from the subject. If a subject responds positively to questions regarding depression, the PI or other psychiatrist will contact the subject in person, by telephone, or by letter to inform the subject of their results and to offer a referral for appropriate consultation. If a subject endorses suicidality or responds positively to questions regarding the harm of self and/or others, the PI or another psychiatrist who is part of the study will be contacted to evaluate what clinical treatment should be recommended. At no time will the subject's relatives be contacted. This is due to the nature of confidential research results.

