**Risk mitigation plans:**

As there will be 3 adverse events of special interest for this study (skin rash, antidepressant-induced mania and suicidal ideation), to mitigate those risks there will be a special monitoring and tracking of those events. At each visit, patients will be assessed for treatment-emergent manic symptoms using the BISS scale, for suicidality using the BISS and C-SSRS scales also and all study clinician will assess for skin rash at each visit. In addition, for populations where the risk of antidepressant-induced mania has been shown to be higher than placebo (bipolar I disorder), patients who are randomized to fluoxetine will be required to stay on a mood-stabilizer during the course of the study to decrease the likelihood of a treatment-emergent mania. A Data Safety and Monitoring Board will review safety data every 6 months.

Date and time of last dose of study medication will be gathered at the 1, 2, 4, 8, 12, and 16 week visits. To ensure compliance with the protocol, subject will bring in their medications at each visit for medication counts. The importance of medication compliance will also be discussed with the subject. To study medication compliance and pharmacokinetic pharmacogenomics blood levels of medication will be measured at week 16.

If participants are on current medications and are otherwise candidates for the study, their primary clinician will be contacted as to the relative merits of enrolling in the study. If it is clinically indicated (i.e. medicines are not helping optimally), the subject will be tapered off all psychotropic medications.

2. Adjunctive and concurrent medications. Adjunctive treatments are those used to manage transient associated symptoms (e.g., insomnia) or transient or longer-term medication side effects (e.g., sexual dysfunction). Adjunctive treatments that are not used to treat depression may be taken during the study. However, drugs in the exclusion criteria for this study may not be used as adjunctive therapies. Participants can participate in the study while receiving concurrent medications for general medical conditions as long as there is no contraindication to their use while taking fluoxetine.

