2. Special attention will be given to participants who develop suicidal ideation. Participants will be closely monitored at visits and also contacted by telephone to ensure medication compliance and participant safety. The SC will be supervised up by the study psychiatrist and principal investigator and will defer to the physician's judgment as needed. The SC will be trained to notify the RC at the time of the clinical visits or the phone interviews if the subject endorses any suicidal ideation or plans. All questionnaires that involve questions related to depression and/or harm to self or others will be reviewed within 1 working day of receipt from the subject. If a subject endorses suicidality with any of the following: Active suicidal ideation as determined by the investigator. If a subject responds positively to questions regarding the harm of self and/or others, the research team will immediately contact the subject in person or by telephone to discuss their responses. If the subject continues to endorse *suicidal ideation*, the investigator will immediately refer subject to the nearest emergency room and/or psychiatric admission on a voluntary or if need be, involuntary basis. If subject denies suicidal feelings and immediate referral to the emergency room deemed un-necessary, the subject will be recommended to get a referral for appropriate psychiatric consultation from the primary provider. Investigators will notify the primary provider about the need for such referral. If the subject does not have a primary provider, the research consultant will provide a referral for psychiatric consultation. The participant will be asked to provide contact information, including an emergency contact. In an emergency (as determined by the PI) the study team will reach out to the emergency contact if the participant cannot be contacted.

**Remuneration:** Participants will be provided study drugs for free and free parking when they come to any of the study visits or study related procedure.: The participant will be paid \$50.00 at the first visit; last visit: \$50.00.

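### The absolute bar on contacting relatives conflicts with the emergency-contact step for a suicidal participant who cannot be reached

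*Combined protocol and SAP*

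**What the plan says.** Two parts of the combined protocol and SAP deal with a participant whose answers indicate suicidality.

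- **Early discontinuation, item 2.** If answers point to harm of self or others, "the research team will immediately contact the subject in person or by telephone to discuss their responses". The item goes on to emergency-room or psychiatric referral, on an involuntary basis if necessary. It then adds "The participant will be asked to provide contact information, including an emergency contact", and finally "In an emergency (as determined by the PI) the study team will reach out to the emergency contact if the participant cannot be contacted".
- **Questionnaires that ask about Depression, plan of management.** The suicidality rule begins "If a subject endorses suicidality or responds positively to questions regarding the harm of self and/or others, the PI or another psychiatrist" and has that psychiatrist decide what treatment to recommend. The next sentence is "At no time will the subject's relatives be contacted". The reason follows: "This is due to the nature of confidential research results".

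Neither part refers to the other.

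**The concern.** The bar has no exception, and it stands in the same paragraph as a suicidality rule, directly after it. The emergency step tells staff to call a person whom the participant has named, and a relative is not ruled out as that person. If a relative is named, obeying the bar means not making the call, and making the call breaks the bar.

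Suicidality is not a side issue in this trial. Risk mitigation plans lists "3 adverse events of special interest for this study (skin rash, antidepressant-induced mania and suicidal ideation"), and the section on serious adverse events handles worsening suicidality as an SAE. What is at stake is whether staff have one clear instruction when a participant may be in danger and does not answer.

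**Working it through.** No arithmetic applies. The check is a comparison of the two rules and a search for text that settles the matter.

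**1. The two rules side by side**

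| | Early discontinuation, item 2 | Plan of management for depression questionnaires |
|---|---|---|
| Situation | Suicidal ideation, including questionnaire answers on harm | Questionnaire answers on depression, suicidality or harm |
| Time to review questionnaires | 1 working day from receipt | 1 working day from receipt |
| Third-party contact | Required with the named contact, if an emergency is declared and the participant cannot be reached | Forbidden with relatives |
| Exception or limit | None concerning relatives | None |
| Reference to the other rule | None | None |

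Both rules cover the same questionnaire review and the same finding, so they cannot be assigned to different situations.

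**2. When they conflict**

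- Participant reachable, or no emergency declared: the emergency step is not triggered, so there is no conflict.
- Emergency, participant unreachable, contact not a relative: the call is required and the bar does not touch it, so there is no conflict.
- Emergency, participant unreachable, contact a relative: one rule requires the call and the other forbids it.

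Only the third case is a contradiction.

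**3. Can the third case arise?** Item 2 puts no limit on who may be named. The participant need not be on site: questionnaires may be reviewed up to 1 working day after receipt, and item 2 itself foresees contact by telephone.

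**4. Does other text settle it?**

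- Stopping Rules for Efficacy and Safety says "Information regarding study participants will not leave the institution in any form that would identify an individual participant". It does not mention emergencies.
- The Subject Privacy and Data Confidentiality items of the Data & Safety Monitoring Plan deal with coding and storage of data. They do not mention emergencies either.
- Risk mitigation plans describes monitoring for suicidality but says nothing about calling third parties.
- Tracking and Retention lists the collection of relatives' and friends' contact details as a possible retention measure. This suggests that a total ban on contact was not intended. Read literally, though, it adds to the tension, and it sets no order of precedence.

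None of these sections reconciles the two rules.

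**The case against.** The best reply is that the intended meaning can be recovered. The bar answers a form prompt about managing questionnaire responses, and its stated reason is the confidentiality of research results. It was probably meant to keep those results from families. The emergency step is narrower and rests on the participant's own choice of contact, so a sensible reader would let it prevail. This is a good account of intent, and it stands as such. But the sentence forbids contact rather than disclosure, it is itself placed in a suicidality rule, and no text gives the emergency step priority.

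A second reply is that the case is rare. Suicidality is rated by BISS and C-SSRS at visits where the participant is with staff. The self-completed WHO-5 is not described as asking about self-harm, and the content of the biobank participant questionnaire, which may be mailed back, is not shown. Immediate contact with the participant and emergency referral are also untouched by the bar. All of this is correct. It limits how often the conflict can arise but does not remove it, since item 2 allows for telephone contact and for a participant who cannot be reached.

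Third, the consent form was not available for this review and might record permission to call the named contact. Such permission would support the call, but it would leave the contrary sentence in the protocol.

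**Conclusion.** The concern holds. Read as written, the two instructions contradict each other when three conditions coincide: the principal investigator has declared an emergency, the participant cannot be reached, and the named contact is a relative. The documents give no frequency for any of the three, so no count is offered.

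This is an internal inconsistency in a safety procedure, with no effect on endpoints, sample size or analysis. The conclusion rests on the protocol text alone and on the absence there of any limit on who may be named. It should be corrected: the trigger is narrow, but the consequence could be grave and the remedy is almost free.

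**What to change.** In the plan of management for depression questionnaires, replace the sentence on relatives with:

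> Questionnaire results are not disclosed to relatives. In an emergency determined by the PI, if the participant cannot be reached, the study team will call the emergency contact the participant named, including a relative (see Early discontinuation, item 2).

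Attach the existing confidentiality reason to the first of these sentences only. The sponsor may also wish to limit what is said in the call to the minimum necessary.

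The cost is one protocol sentence replaced by two. Visits, data collection and analysis stay as they are.
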